The PRISM (Promoting Resilience in Stress Management) intervention is an evidence-based program that builds resilience. This program was developed in adolescent and young adult oncology, and utilizes centrally-administered skills-based coaching to bolster positive psychological tools known as resilience resources. These resources include stress management, goal-setting, and positive reframing. Previous studies using this intervention have found PRISM to be successfully administered remotely and it has improved resilience, psychological distress, hope, and quality of life.¹⁰ Among adult caregivers, PRISM has shown to improve resilience, self-efficacy, and engagement with medical care.¹¹ While PRISM successfully targets distress and associated downstream consequences known to be experienced by breast cancer survivors, it has not been utilized in adults with cancer or in marginalized communities. Adapting this intervention to this context will require the testing of the intervention and, importantly, tailoring to meet the needs of women with breast cancer, particularly those of marginalized populations who may uniquely benefit from this intervention.

2. Objective

This single-arm pilot study will (1) test feasibility, acceptability, and appropriateness of the PRISM intervention in individuals with breast cancer, (2) elicit patient perspectives on elements for future adaptation or expansion to meet the unique needs of women with breast cancer, (3) assess trajectory of patient-reported outcomes and biological measures of stress for patients with breast cancer receiving the PRISM intervention.

3. Hypothesis:

We hypothesize that PRISM will be feasible, acceptable, and appropriate for individuals with breast cancer.

4. Approach

3.1 *Study eligibility criteria, screening procedures, recruitment:* There will be two cohorts in this study. Cohort 1 will include women undergoing chemotherapy for early-stage breast cancer. Cohort 2 will include women undergoing treatment for metastatic breast cancer. Patients who do not speak English will be excluded. The study team will identify 30 women with early-stage disease (Cohort 1) and 10 women (Cohort 2) with metastatic disease to

participate through the review of daily clinic lists, coupled with discussions with clinical teams. We anticipate minimal drop-out since patients will still be in an active phase of cancer treatment in the initial year after diagnosis. However, if patients drop out of the study, they will be replaced to achieve a total number of patients for each cohort. Across the entire study, we will sample such that we include at least 20 women who are Black or African American, ten women living in areas of higher disadvantage (defined using Area Deprivation Index), and five women with dependent children. Given the intersectionality of these characteristics, patients may represent more than one target population. Women will be approached in clinic by a study coordinator who will explain the study and obtain informed consent.

3.2 Study Procedures-Patient and Clinic Characteristics: A REDCAP database will be used to track patients approached, enrolled, and completing each portion of the study (blood/nail collection, patient reported outcomes (PROs), and intervention components). For patients enrolling in the study, a unique study ID will be created for each patients. The following patient and clinical characteristics of participants who enroll will be abstracted from the medical record: age at diagnosis, sex, race and ethnicity, insurance status, address, breast cancer stage, treatments received, BMI, blood pressure, prior diabetes/hypertension/cholesterol treatment. At the time of enrollment, a waist circumference will be captured using a tape measure (documented in cm).

| Table 1. Promoting Resilience in Stress Management (PRISM) intervention content | | | |
|--|--|------------------------|--|
| Session Focus* | Details | Format | Stress and Coping Theory Constructs |
| 1. Getting to Know You | Provide information about the logistics of the PRISM program, explain it in detail, and answer any questions the participant may have. | 1:1 (video) | |
| 2. Stress Management | Relaxation strategies (i.e., deep breathing), Mindfulness techniques | 1:1 (video) | Situational factors |
| 3. Catching Your Thought | Recognizing and reframing negative thoughts | 1:1 (video) | Coping processes |
| 4. Goal Setting | Setting SMART goals, planning for roadblocks | 1:1 (video) | Situational factors |
| 5. Finding the Positives | Identifying gratitude or meaning from illness experience | 1:1 (video) | Coping processes |
| 6. Coming Together | Discussion about what was learned, what worked, how loved ones can help (optional) | Family meeting (video) | Situational factors and Coping processes |
| Advance Care Planning | Discussion of advance care planning (optional) | | |
| Skill Practice | Between-session exercises to practice, further develop and track skills | Digital app | |

*Sessions 1-6 are delivered every 1-2 weeks.

3.3 Intervention: PRISM is a manualized, brief, skills-based intervention targeting four resilience resources (stress-management, goal-setting, cognitive-reframing, meaning-making) consistently associated with improved psychosocial outcomes (**Table 1**).¹⁰⁻¹² Its content has been validated with proof-of-concept and pilot studies in diverse populations, including Adolescents and Young Adults (AYAs) with cancer, diabetes, or cystic fibrosis; parents of children with cancer or diabetes; interdisciplinary health-care professionals during the COVID-19 pandemic; adults with congenital heart disease; and caregivers of adult patients from marginalized background who experience racism.⁷⁹ The program has proven efficacy in randomized trials among these populations.^{11,12} The content is understandable and applicable across multiple stressful situations, thus creating the potential for broad, ground-breaking impact. Content will all be provided by video.

Specifically, PRISM is delivered by trained intervention staff (called “coaches” within the PRISM program). Each coach receives >8 hours of standardized training, including role-playing and trouble-shooting, to demonstrate competency and mastery of the program script. Each PRISM session is audio-recorded to monitor for script-fidelity; the senior coach training reviews and scores each recording for fidelity using a standardized tool. In cases where coaches do not receive a score of 80% or higher, they receive additional training and supervision. In the history of the PRISM program’s experience and >500 program deliveries, to date, no such remediation has yet been necessary.

Intervention sessions are described in detail in the attached Appendix A (PRISM manual). They are scheduled approximately weekly to every-other-week, depending on participant preference to optimize feasibility and completion. Briefly, for each session, coaches (i) ensure a private video conference to enable participation and conversation; (ii) review session content and format; (iii) teach and practice a particular resilience skill; and (iv) plan opportunities to practice the skill. Session 1, Stress-Management, involves mini-skills such as deep breathing, guided imagery, and mindfulness. Session 2, Goal-Setting, involves deconstructing and reconstructing goals to make them “SMART” (Specific, Measurable, Actionable, Realistic, and Time-Dependent). The session also includes exercises to plan for challenges and alternative strategies. Session 3, Cognitive Restructuring, involves recognizing negative self-talk and reframing impressions of negative experiences to make them feel more manageable. Session 4, Meaning-Making, involves exercises to find gratitude and purpose in the context of adversities like cancer. Session 5 (optional), Coming Together, is optional and involves the participant and their loved ones discussing the program and lessons-learned. Session 6 (optional) involved advance care planning to discuss future goals related to medical care.

Throughout the program, participants will have access to the award-winning PRISM smartphone app. This program provides practice opportunities for all of the skills, plus an embedded journal to catalogue goals, lessons-learned, and gratitudes; a library of related, evidence-based resources; tracking tools to monitor one’s own stress and resilience.

The total PRISM intervention lasts 6-8 weeks, and the app is available thereafter, indefinitely.

3.4 Study Procedures-Surveys: Following enrollment, the participants will be asked to complete baseline surveys at the time of consent. The research coordinator will register the patient, providing the study ID, patient phone number, and email address for survey completion to the PRO Core team at the University of North Carolina. Surveys will be

completed electronically, when possible, but paper and telephone-based options will be available for patients not able to complete electronically. Baseline surveys should be completed within 90 days of completion of definitive therapy (chemotherapy, radiation, or surgery) for Cohort 1 (early stage) and at any time post metastatic diagnosis for Cohort 2 (metastatic). We will allow people to enroll during ongoing maintenance therapy with non-cytotoxic therapies including endocrine therapy, targeted therapy (e.g. Her2-targeted therapy) or immunotherapy. Patients will be asked to complete a follow-up survey after completion of the PRISM intervention, with a goal completion of within 60 days. We will make up to 5 attempts to reach patients if they do not complete their survey. The survey includes 114 questions at baseline and 106 questions at follow-up on feasibility, acceptability, appropriateness, recent stressors, fear of recurrence, anxiety, depression, social determinants of health, spirituality, resilience, posttraumatic growth, patient activation, and quality of life (**Table 2**). The survey is expected to take approximately 30-40 minutes to complete.

Survey responses will be captured using a database hosted by the University of North Carolina PRO Core. The staff at PRO Core will contact participants once prior to each survey due-date, and up to 4 times thereafter for missed surveys. PRO Core will oversee data monitoring and quality. PRO Core adheres to best practices for data security and privacy. PRO Core is accessed through a web interface using a secure, authenticated login. Data are stored in a secure enterprise-level Oracle database; the databases and web servers are hosted by the UNC Center for Bioinformatics. Data transmitted between the server and end-users are encrypted using SSL, and all databases are encrypted. PRO Core will store patient data in a secure database identified by a coded study ID. Upon study conclusion, the de-identified dataset will be transferred to UAB via secure transfer and stored in a password protected file for analysis.

3.5 Study Procedures- Biological Specimens (Cohort 1 Early Stage Breast Cancer Patients Only):

Blood samples:

Blood samples will be collected at baseline and approximately 6 months after surgery (post PRISM intervention, aligned with standard of care appointment where possible).

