3.7 Compensation: Participants who complete biomarker and survey portions of the study will receive a \$50 gift card upon completion. Patients who complete the interview will receive an additional \$50 upon completion (\$100 total for Cohort 1, \$50 for Cohort 2).

3.8 Quantitative Analysis: Cohorts will be analyzed both separately and together. The primary outcome is feasibility, which will be defined as 70% of women completing all intervention components and 70% of survey time points (baseline, post-surgery, post intervention)

being completed. Secondary endpoints will include implementation outcome measures by Weiner, which will evaluate the acceptability, appropriateness, and feasibility (survey-based) of interventions.²⁰ Acceptability of Intervention Measure (AIM), Intervention Appropriateness Measure (IAM), and Feasibility of Intervention Measure (FIM) are implementation measures with four-items each, and a response scale ranging from 1 to 5 (1 = Completely disagree, 2 = Disagree, 3 = Neither agree nor disagree, 4 = Agree, 5 = Completely agree).²⁰ Scores for each measure are calculated by averaging responses.²⁰ An average of 4 or greater on each measure (AIM, IAM, FIM) will be considered acceptable, appropriate, and/or feasible.

We will also capture the following measures for future comparative efficacy trial:

- **Fear of recurrence** will be measured using the Fear of Cancer Recurrence Inventory Short Term (FCRI_SF) which is scored from 0 to 4 (0 = Not at all, 1 = A little, 2 = Somewhat, 3 = A lot, 4 = A great deal)¹³.
- **Patient depression** will be measured using the Patient Health Questionnaire depression scale¹⁴, which is a 2 questions screener with 6 additional questions for an 8 question scale with a cut-point of greater than or equal to 10 being defined as current depression.
- **Patient anxiety** will be measured using the General Anxiety Disorder-7 scale,¹⁵ which is a 7 item scale with scores of 0-4 signifying minimal anxiety, 5-9 mild anxiety, 10-14 moderate anxiety, and greater than 15 severe anxiety.
- **Resilience** using the Connor-Davidson Resilience scale which has 10 items each carry a 5 point range (0 = Not true at all, 1 = Rarely true, 2 = Sometimes true, 3 = Often true, and 4 = True nearly all of the time; total scores range from 0-40, and higher score indicate higher resilience)¹⁶

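### Cohort 1 is defined by ongoing chemotherapy in section 3.1 but by completion of definitive therapy in section 3.4; the two rules overlap only in part and are not reconciled

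*Combined protocol and SAP*

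**What the plan says.** All references are to the combined protocol and SAP.

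- **Section 3.1 (eligibility):** "Cohort 1 will include women undergoing chemotherapy for early-stage breast cancer". The same section expects little drop-out because "patients will still be in an active phase of cancer treatment in the initial year after diagnosis".
- **Section 3.4 (surveys), timing relative to consent:** "the participants will be asked to complete baseline surveys at the time of consent".
- **Section 3.4, Cohort 1 window:** "Baseline surveys should be completed within 90 days of completion of definitive therapy (chemotherapy, radiation, or surgery) for Cohort 1 (early stage"). The next sentence reads "We will allow people to enroll during ongoing maintenance therapy with non-cytotoxic therapies" and gives endocrine, targeted and immunotherapy as the examples.
- **Section 3.5 (biological specimens, Cohort 1 only):** "Blood samples will be collected at baseline and approximately 6 months after surgery (post PRISM intervention").
- **Section 3.8 (primary outcome):** the survey part of feasibility counts "70% of survey time points (baseline, post-surgery, post intervention"). The pre-post model in the same section uses two time points, and Table 2 has only baseline and follow-up columns.

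**The concern.** Because baseline is taken at consent, the 3.4 window works in practice as an enrolment window. A coordinator screening clinic lists for Cohort 1 therefore has two rules, one requiring chemotherapy to be under way and the other built around definitive therapy being finished.

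Two things are at stake. The primary outcome is feasibility, and completing a 6-8 week coaching programme during chemotherapy is a different question from completing it afterwards. If the enrolled group depends on which sentence the site followed, the population to which a 70% completion result applies is undefined. Second, the third objective is the trajectory of patient-reported outcomes and stress biomarkers, estimated as change from T1 with no control arm. If T1 falls during chemotherapy for some women and after it for others, change over PRISM is mixed with differing amounts of recovery from treatment. Section 3.8 plans breakdowns by race, area of residence and dependent children, but none by treatment phase.

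**Working it through.** **1. The two rules side by side.** The point rests on comparing text. Reading the 3.4 window as running after completion:

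| Woman at consent | Section 3.1 | Section 3.4 window |
|---|---|---|
| On chemotherapy before surgery, no modality finished | Met | Not met |
| On adjuvant chemotherapy, within 90 days of surgery | Met | Met if finishing any one listed modality is enough; not met if all must be finished |
| All chemotherapy and other definitive therapy finished within the last 90 days, with or without maintenance | Not met | Met |

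The overlap is the middle row, and it depends on how the word joining the three modalities is read. No passage settles that.

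**2. Share of the trial affected.** Cohort 1 is 30 women and Cohort 2 is 10, so the conflicting rules govern 30/40 = 75% of planned enrolment. How many women would actually fall in each row cannot be derived from the documents.

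**3. The surgery-anchored time points.** A post-surgery survey listed between baseline and post intervention, and a second blood draw dated from surgery, fit a baseline before surgery more easily than one after all definitive therapy. To see whether the blood draw fits the 3.4 window, take completion to mean the end of all definitive therapy (day 0), let PRISM start on the day of baseline, use the stated 6-8 weeks (42-56 days), and count 6 months as 183 days.

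- Baseline on day 90: PRISM ends on day 90 + 42 = 132 to 90 + 56 = 146. The 6-month draw precedes the end of PRISM if surgery was more than 183 - 146 = 37 days (8-week course) or 183 - 132 = 51 days (6-week course) before day 0.
- Baseline on day 0: PRISM ends on day 42 to 56, and the corresponding limits are 183 - 56 = 127 and 183 - 42 = 141 days.

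So for some sequences permitted by 3.4, a draw cannot be both about 6 months after surgery and post PRISM. The protocol's timing is approximate, so these limits are indicative.

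**4. The plan's own precision figures.** Section 3.8 gives 95% half-widths of 0.38, 0.35 and 0.30 for correlations of 0.5, 0.6 and 0.7. With n = 0.70 × 40 = 28 and half-width = t(0.975, n-1) × √(2(1-ρ)) / √n, I get 0.388, 0.347 and 0.300, which agree to within about 0.01. Nothing in that formula depends on how Cohort 1 is defined, so these figures are not in question.

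**The case against.** The strongest reply is that the two sections can be read together. Section 3.4 joins chemotherapy, radiation and surgery with an *or*, so a woman on adjuvant chemotherapy shortly after surgery meets both. It also does not say whether the 90 days run before or after completion; if they run both ways, women near the end of chemotherapy qualify too. This stands against anyone who would infer that the two populations are mutually exclusive. It does not remove the conflict. Even on the widest reading, a woman who has finished all chemotherapy fails 3.1, and one with more than 90 days of chemotherapy left and nothing else completed fails 3.4.

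Three other stronger readings are tempting and not supported:

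- *That 3.4 excludes women on cytotoxic treatment.* The maintenance sentence is permissive and states no exclusion. It does lean against the overlap reading, since there would be little reason to single out non-cytotoxic therapy if chemotherapy could also be ongoing.
- *That the drop-out rationale contradicts 3.4.* Active treatment in the first year can include the maintenance therapy that 3.4 allows, and the sentence is not limited to Cohort 1. It needs checking after the fix.
- *That the bias can be stated in standard deviations.* The documents give neither a recovery effect nor a mix of treatment phases. Nor would the 3.8 half-widths be the right yardstick for a Cohort 1 shift, since they are for N = 40. The same formula for Cohort 1 at 70% completion (n = 0.70 × 30 = 21) gives about 0.46, 0.41 and 0.35.

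It is also fair to say that the pre-post results are descriptive, that no formal testing is planned, and that any single-arm design mixes recovery with intervention. That limits the harm to the change scores. It does not answer the feasibility point, which concerns the primary outcome.

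**Conclusion.** The inconsistency is real and should be corrected. Section 3.1 and section 3.4 give different, partly overlapping screening rules for 30 of 40 participants, and the surgery-based time points in 3.5 and 3.8 add a third anchor. Following the plan as written leaves open who is enrolled in Cohort 1, what T1 means for the patient-reported and biomarker change, and for which population feasibility is shown.

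This rests on two readings: that baseline at consent makes the 3.4 window an enrolment window, and that 3.1 means chemotherapy is ongoing when a woman is enrolled. Section 3.1 itself gives no baseline time, so the timing conflict comes from combining sections. The documents do not show which population is intended, and no numerical bias can be attached.

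**What to change.** The sponsor should choose the intended Cohort 1 population and state it once, with one anchor date, and then bring four places into line with it: the criterion in 3.1, the baseline window in 3.4 (saying whether it runs before or after the anchor, and whether one modality or all must be complete), the second blood draw in 3.5, and the survey time points in the 3.8 primary outcome. The drop-out rationale in 3.1 should then be checked against the chosen population.

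At baseline, record treatment phase and the date of last definitive therapy, and describe Cohort 1 by phase. Description is enough; with 30 women, formal comparison by phase is not called for. Recovery from treatment will still be mixed with PRISM, but a uniform or recorded phase makes the estimates interpretable.

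The cost is a protocol wording amendment plus a small addition to data collection. Section 3.2 already abstracts treatments received but does not list their dates. For women already enrolled, if there are any, the dates would have to be taken from the medical record.

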3.6 Study Procedures- Post-intervention Interview (Both Cohorts) Upon completion of the whole intervention, participants will participate in a 30 minute to 1-hour semi-structured interview (Appendix B) to elicit perspectives on psychological state, intervention feasibility and acceptability, and areas for expansion of the intervention to better meet the needs of women with breast cancer, all the while with a focus on equity. A semi-structured interview will be conducted by a trained qualitative interviewer either in person or virtually using Zoom or by phone based on patient choice. Interviews will be audio recorded, transcribed verbatim, and stored in a secure, password-protected folder. Participants who do not complete the intervention or complete surveys will also be asked to participate in interviews to explore barriers to completion and opportunities for improvement.

| Table 2. Primary and secondary outcomes. | | | | | |
|---|--|-----------------|------------------|------------------------|--|
| Domain | Instrument or Source | Baseline | Follow-up | Number of items | Expected length of time to complete |
| Demographics | Study-specific questionnaire | X | | 9 | 2 minutes |
| Social determinants of health | CMS Health Related Social Needs | X | | 11 | 2-3 minutes |
| Spirituality | FACIT-SP | X | X | 12 | 2-3 minutes |
| Fear of cancer recurrence* | Fear of Cancer Recurrence Inventory Short Form (FCRI-SF) ¹³ | X | X | 12 | 2-3 minutes |
| Depression | Patient Health Questionnaire depression scale ¹⁴ | X | X | 8 | 2 minutes |
| Anxiety | General Anxiety Disorder-7 ¹⁵ | X | X | 7 | 2 minutes |
| Resilience | Connor Davidson Resilience Scale -10 ¹⁶ | X | X | 10 | 2-3 minutes |
| Post-traumatic growth | Post-Trumatic Growth Inventory ¹⁷ | X | X | 21 | 3-4 minutes |
| Patient activation | Patient Activation Measure (PAM) ¹⁸ | X | X | 13 | 2-3 minutes |
| Quality of life | PROMIS Global Short Form ¹⁹ | X | X | 10 | 2-3 minutes |
| Life stressor question | Study Specific Survey | X | X | 1 | 30 seconds |
| Acceptability | Acceptability of Intervention Measure (AIM) ²⁰ | | X | 4 | 1-2 minutes |
| Appropriateness | Intervention Appropriateness Measure (IAM) ²⁰ | | X | 4 | 1-2 minutes |
| Feasibility | Feasibility of Intervention Measure (FIM) ²⁰ | | X | 4 | 1-2 minutes |

*Only administered to patients with early stage breast cancer

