No formal power calculation is needed for this pilot study as feasibility is defined by patient participation and completion of surveys. Following NIH guidelines, no formal testing will be conducted. Uncertainty of pre-post change estimates will be measured with 95% confidence intervals. Assuming 70% completion in the full sample (N=40), a standardized outcome, and intra-subject correlation values 0.5, 0.6, and 0.7, the upperbound half-widths of 95% confidence intervals for pre-post change are 0.38, 0.35, and 0.30, respectively. These provide reasonable ranges for potential values of change that can be expected in a future project (computations in PASS 23 software).

3.9 *Biomarker evaluation:* Data from biomarkers and ePROs will be merged with demographic data using a study ID and date of collection. We will assess the relationship between biomarker outcomes and patient-reported outcomes. We will assess for correlational trends that would support evaluation in a larger cohort. We will examine distribution and ranges of biomarker data and determine whether variance stabilizing transformations are needed such as a natural logarithm, prior to analysis. As described above, we will employ a similar quantitative approach to compare pre/post intervention differences in assessed levels of cortisol, allostatic load, DAMPs and inflammatory response biomarkers (cytokines).

3.10 *Data linkage:* Both ePRO data and the data from biospecimens will be labeled using a Study ID. A separate tracking log will be kept with Study ID and MRN at UAB. This tracking log will be used to link datasets for analytic purposes.

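### Drop-outs are replaced, but nothing keeps them in the denominator of the primary completion percentage, so feasibility will usually read too high if it is taken on the refilled cohorts

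*Combined protocol and SAP*

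**What the plan says.** Section 3.1 sets targets of 30 women in Cohort 1 and 10 in Cohort 2 and adds that "if patients drop out of the study, they will be replaced to achieve a total number of patients for each cohort". It gives no drop-out rate, only an expectation: "We anticipate minimal drop-out since patients will still be in an active phase of cancer treatment".

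Section 3.8 makes feasibility the primary outcome and defines it as "70% of women completing all intervention components and 70% of survey time points". It does not say which women form the denominator. It also says "Cohorts will be analyzed both separately and together". The precision statement later in the same section begins "Assuming 70% completion in the full sample (N=40"), and 40 is the sum of the two refilled targets.

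Three other statements bear on the point:

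- Section 3.2 has a REDCap database that will "track patients approached, enrolled, and completing each portion of the study".
- Section 3.6 says "Participants who do not complete the intervention or complete surveys will also be asked to participate in interviews".
- Section 3.8 says that the models use all available data.

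**The concern.** A woman who leaves before finishing PRISM is a feasibility failure. The replacement rule takes her out of the cohort and puts another woman in her place. Unless something keeps her in the percentage, the primary outcome is calculated after some of the failures it should count have been swapped out.

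None of the three other statements settles this. REDCap tracking makes an all-enrolled count possible but does not assign it to the endpoint. The interviews with non-completers are qualitative and do not enter the percentage. The sentence on available data concerns the pre-post mixed models.

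Feasibility is the main result of this pilot. It is read against a fixed 70% line, and Section 3.13 says the findings will inform a later comparative efficacy trial. A completion rate that reads too high would make that trial look easier to run than it is. If the denominator is chosen after the data are in, the choice itself could decide whether 70% is met.

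**Working it through.** **Inputs from the plan.** Targets N = 30, 10 and 40 (Section 3.1); threshold 70% (Section 3.8), which means at least 21/30, 7/10 or 28/40.

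**Assumptions.** The number of replaced non-completers, r, and the true completion proportion among all enrolled women, p. The plan gives neither.

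**The plan's own figure.** No calculation is given for the primary percentage. The only computed figures are the half-widths for pre-post change: 0.38, 0.35 and 0.30. With n = 0.70 × 40 = 28 and half-width t(0.975, 27) × √(2(1 − ρ)/28), where t = 2.052, I get 0.388, 0.347 and 0.300 for ρ = 0.5, 0.6 and 0.7. These agree closely, so the plan does take 70% of 40.

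**Step 1: effect on the ratio.** With x completers in the refilled cohort, the reported rate is x/N and the all-enrolled rate is x/(N + r). The smallest r that takes the result below 70% is:

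| Reported | r | All enrolled |
|---|---|---|
| 28/40 = 70.0% | 1 | 28/41 = 68.3% |
| 29/40 = 72.5% | 2 | 29/42 = 69.0% |
| 30/40 = 75.0% | 3 | 30/43 = 69.8% |
| 32/40 = 80.0% | 6 | 32/46 = 69.6% |
| 21/30 = 70.0% | 1 | 21/31 = 67.7% |
| 7/10 = 70.0% | 1 | 7/11 = 63.6% |
| 8/10 = 80.0% | 2 | 8/12 = 66.7% |

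**Step 2: chance of reaching the line.** If r non-completers are replaced, all p(N + r) expected completers are among the N retained, so the apparent rate is p(N + r)/N. The chance of reaching the line is the binomial probability of at least 0.7N completers at that rate. For N = 40 and p = 0.60, r = 0, 1, 2 gives apparent rates 0.600, 0.615, 0.630. This covers the intervention-component criterion only.

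| N | True p | r = 0 | r = 1 | r = 2 |
|---|---|---|---|---|
| 40 | 60% | 13% | 17% | 23% |
| 40 | 70% | 58% | 67% | 76% |
| 40 | 80% | 96% | 98% | 99% |
| 30 | 60% | 18% | 24% | 32% |
| 10 | 60% | 38% | 54% | 70% |

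With four replaced (4 of 44 enrolled, about 9%), N = 40 and p = 0.60, the apparent rate is 0.60 × 44/40 = 0.66 and the chance is 36%.

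**Step 3: how likely is any drop-out?** The chance of at least one drop-out among 40 women is 1 − (1 − d)^40: 33%, 55% and 87% at assumed drop-out rates d of 1%, 2% and 5%.

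**Step 4: the exception.** Study duties continue after PRISM: a follow-up survey, an interview and, in Cohort 1, a second blood draw ("Blood samples will be collected at baseline and approximately 6 months after surgery"). A woman can finish PRISM, then withdraw and be replaced. If that is the one replaced woman, 28/40 becomes 29/41 = 70.7%, and leaving her out lowers the rate. This is why the bias is usual rather than certain.

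**Step 5: the survey criterion.** Suppose all 40 women give a baseline survey, 28 give every later one, and four replaced women gave a baseline only. With the two time points of Table 2, (40 + 28)/80 = 85.0% becomes (68 + 4)/88 = 81.8%. With the three listed in Section 3.8, (40 + 56)/120 = 80.0% becomes (96 + 4)/132 = 75.8%. Both still pass, so this criterion is less sensitive.

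**The case against.** The plan is silent on the denominator; it does not say that replaced women are excluded. The plain reading of women could be all women in the study, and REDCap holds what that reading needs. The N=40 appears in a precision calculation for pre-post change, and by assuming 70% completion it keeps 12 non-completers among the 40. Non-completers who stay in the study are not replaced, so only formal drop-outs are at issue, and few are expected. Nor is 40 a firm final number, since Section 3.12 allows more participants if thematic saturation is not reached. No passage ties a go/no-go decision to the 70% line, no testing is planned, and a separate 70% verdict for each cohort is inferred from the statement that cohorts are analysed separately. The largest effects arise at exactly 70% or in a cohort of 10, where two replacements are 2 of 12 enrolled (17%), hardly minimal.

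Most of this limits the size of the problem and is accepted. The bias depends on the refilled denominator being used, and the N=40 only suggests that it would be. What remains is that a stated rule removes women the primary outcome should count, and no passage puts them back. An expectation of few drop-outs does not define a denominator. The absence of a test does not help either, because the bias is in the estimate itself.

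**Conclusion.** The concern holds and should be fixed. Replacement is stated, the denominator of the primary percentage is not, and taking it on the refilled cohorts will usually overstate completion. Near the line one uncounted non-completer changes the reading; at 32/40 it takes six. The effect matters mainly when true completion is near or below 70%, and most in Cohort 2. At about 80% or more the pooled reading is unlikely to change, and if nobody drops out there is no bias.

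The probabilities are illustrative. They rest on assumed numbers replaced, independent women with a common completion probability, and replaced women who had not finished PRISM, and they cover the component criterion alone. The harm is a biased feasibility estimate passed on to the planning of a later trial, not a wrong formal decision.

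**What to change.** State in Sections 3.1 and 3.8 that the denominator of both feasibility percentages, by cohort and pooled, is every woman who consented and enrolled. This includes women who dropped out as well as their replacements, each counted by what she actually completed. Report the number replaced in each cohort. Settle this before results are seen.

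Replacement can still be used to reach the target numbers for the pre-post, biomarker and interview analyses. A completion rate among women who started PRISM can be shown beside the primary figure as supportive.

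The cost is one or two sentences of protocol text. No new data are needed, since enrolment and completion are already tracked. The only downside is that the reported feasibility may be slightly lower.
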